9.7.1 Safety Analysis

The serious adverse event will be coded by MedDRA (Medical Dictionary for Regulatory Activities).

The cumulative total number and percentage of patients reporting serious adverse event and adverse drug reaction will be tabulated. The reason for treatment discontinuation will also be summarized.

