9.2.2 Drop-Out Subjects

Once a subject is dropped out from the study, no further information for that subject will be collected. However, the reason for drop-out will be reported and serious adverse events will be reported to AbbVie until 30 days following the intake of the last dose of adalimumab.

Subjects will be dropped out from the study:

- 1) If the subjects choose to withdraw from the study
- 2) Where ethical or practical conflicts hinder the procedure of the study, and such cases will be determined based on the investigator's judgment
- 3) In case of Adalimumab discontinuation at any point during study period

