9.2.3 Investigator Selection Criteria

The rheumatologist will be selected based on the following criteria:

- Those who work in hospitals that have sufficient numbers of eligible patients.
- Those who agree to devote adequate time to conduct the study in accordance with the protocol.
- Those who will report any serious adverse events in patients using an AbbVie product to AbbVie in accordance with the protocol.

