9.3 Variables

Participating subjects will be followed up at week 12, 28, 36, and 52 for 12 months after baseline. At baseline, demographics, disease and medication related data, the presence of extra-axial symptoms such as peripheral arthritis, enthesitis and dactylitis will be collected.

On every follow-up visit, BASDAI 50 will be measured to observe the effectiveness of AS. Also, the change of MASES, TJC_s (0 to 46), SJC_s (0 to 44), Dactylitis score and the presence of plantar fascia will be evaluated to investigate the effectiveness of adalimumab on EAMs.

After baseline visit, if subjects have extra-axial symptoms other than Enthesitis, Peripheral arthritis and Dactylitis, relevant data will be collected.

Enthesitis is defined as at least 1 inflamed enthesis in the Maastricht Ankylosing Spondylitis Enthesitis Score (MASES, 0 to 13) or of the plantar fascia of the foot. Peripheral arthritis is defined as at least 1 of swollen joint counts (SJC, 0 to 44, excluding hip joints). Dactylitis will be measured by a simple count of dactylitic digits.

Patients will be administered adalimumab 40 mg every other week in addition to their preexisting anti-rheumatic treatment for a study period of 1 year as per Korean AS reimbursement guideline.

In the event of Adalimumab discontinuation, the reason for discontinuation will be collected. If the reason for treatment discontinuation is due to an adverse event, the event will be collected.

The following variables will be collected at baseline, and every follow-up visit thereafter during the study period.

Baseline

- 1) Demographics: Age, Gender, Family History of AS, Co-morbidity
- 2) Previous AS-related medication (medication, dosage)
- 3) Concomitant medication
- 4) BASDAI 50
- 5) Extra-axial symptoms: Enthesitis, Peripheral arthritis and Dactylitis (presence or absence)
- 6) Extra-axial symptoms assessment: MASES, enthesitis of the plantar fascia, TJC^s and SJC^s, Counts of dactylitic digits
- 7) Adalimumab administration

Week 12, 28, 36 and 52 after baseline

**Window period for each follow up visit will be ± 4 weeks.*

- 1) BASDAI 50

- 2) Extra-axial symptom assessment: MASES, enthesitis of the plantar fascia, TJC^s and SJC^s, Counts of dactylitic digits
- 3) The change of AS-related medication (If applicable)
- 4) Extra-axial symptoms excluding Enthesitis, Peripheral arthritis and Dactylitis (If applicable, such as IBD, uveitis, etc.)

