9.4 Data Sources

The investigator should maintain source documents for each subject in the study, consisting of medical records containing demographic data, and other information to be collected.

Case Report Forms will be supplied by AbbVie, and used to transmit the collected information during this study to AbbVie.

Case report forms will include patient demographic information, e.g., gender, age, unique patient study number, family history of AS, co-morbidity and the information to be evaluated according to the study protocol. Case report forms will maintain patient confidentiality, e.g., patient names must not be collected and full date of birth must not be collected (age is acceptable). The investigator or staff under his/her supervision must complete the case report forms, and neither AbbVie nor any agents acting on behalf of AbbVie may complete the case report forms.

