9.6 Data Management

Investigator should complete, sign and date the CRFs accurately. All CRFs must be legible and completed in indelible ballpoint ink. Corrections to the CRFs should be made with a single line, be initialed and dated, with the reason for changes given. Data are not to be obliterated by blacking out, correction fluid, or by erasing the original entry.

At the completion of the study, the completed signed and dated case report forms of all enrolled patients should be provided to AbbVie by the investigator. ONLY data specified in the protocol should be collected and submitted to AbbVie.

CRAs or their designees will be responsible to review the collected case report forms for completeness and conclusiveness.

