11.4 Serious Adverse Event Collection Period

Serious adverse events will be reported to AbbVie from the time the physician obtains the patient's authorization to use and disclose information (or the patient's informed consent) until 30 days following the intake of the last dose of physician-prescribed treatment.

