11.5 Serious Adverse Event Reporting

In the event of a serious adverse event, the physician will:

- For events from patients using and AbbVie product - notify the AbbVie contact person identified below within 24 hours of the physician becoming aware of the event.

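### Section 9.7.1 plans an unqualified adverse drug reaction percentage, but the protocol states no collection route for non-serious events that are not the reason for stopping adalimumab

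*Combined protocol and SAP*

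**What the plan says.** The planned output in section 9.7.1 (Safety Analysis) is: "The cumulative total number and percentage of patients reporting serious adverse event and adverse drug reaction will be tabulated". Nothing limits the reactions to be counted to serious ones or to those that ended treatment. The same section plans MedDRA coding for SAEs only, and a summary of the reasons for stopping treatment. The term ADR is expanded in section 2.0, and adverse reactions appear in the heading of section 11.0, but no section defines the term.

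The protocol states two collection routes.

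- **SAEs.** Section 11.4: "Serious adverse events will be reported to AbbVie from the time the physician obtains" the patient's authorization, ending 30 days after the last dose. Section 11.5 opens with "In the event of a serious adverse event, the physician will" and asks for notification within 24 hours. For drop-outs, section 9.2.2 says that "the reason for drop-out will be reported and serious adverse events will be reported to AbbVie until 30 days following" the last dose. Section 9.2.3 selects investigators who commit to this route: "Those who will report any serious adverse events in patients using an AbbVie product to AbbVie in accordance with the protocol".
- **Events that end treatment.** Section 9.3: "If the reason for treatment discontinuation is due to an adverse event, the event will be collected".

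Two further sections bear on what the case report form (CRF) may hold. Section 9.6 says "ONLY data specified in the protocol should be collected and submitted to AbbVie". Section 9.4 describes the CRF as carrying demographic information and "the information to be evaluated according to the study protocol".

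**The concern.** A percentage of patients with an event means what its label says only if all events of that kind are collected. Here the output names ADRs without qualification, while the stated collection rules cover a subset of adverse events. A patient with, say, a related but non-serious event who stays on treatment would count as having no ADR.

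What is at stake is how the safety table is read. Someone who meets an ADR percentage beside an SAE percentage would naturally take it as the share of patients with any reaction to adalimumab, and might compare it with ADR percentages from studies that collected all adverse events. The primary result, the frequency of extra-axial manifestations at baseline, is not touched.

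**Working it through.** The plan gives no ADR figure to reproduce, so the check sets the sections side by side.

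**Step 1: every place where an adverse event could enter the data.**

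- Section 9.3 lists the variables at baseline and at weeks 12, 28, 36 and 52. Neither list has an adverse event or ADR item. The nearest is the item on other extra-axial symptoms, such as IBD or uveitis. These are recorded as features of the disease, with no stated assessment of relationship to the drug.
- Section 9.1 plans one follow-up about 30 days after the last dose, but section 9.3 lists no variables for it.
- Section 11.2 grades the severity of SAEs and of any adverse event collected as a data point. The only non-serious events that the protocol names for collection are those that were the reason for stopping.
- Section 11.3 says how to judge relationship. It does not say which events to collect.
- Section 11.6 concerns pregnancy. The table of contents lists no section on reporting of non-serious events.

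**Step 2: cross-classify related events by stated route.**

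| Related event | Reason for stopping adalimumab | Not the reason for stopping |
|---|---|---|
| Serious | route (9.2.2, 9.3, 11.4, 11.5) | route (9.2.2, 11.4, 11.5) |
| Non-serious | route (9.3) | no stated route |

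Three of the four classes have a route and one has none.

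**Step 3: who falls in the fourth class.** There are three groups:

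- patients who have the event and continue adalimumab;
- patients who have the event but stop for another cause, such as their own choice or the investigator's judgment (both listed in section 9.2.2);
- patients who have the event after drop-out, when section 9.2.2 ends collection except for the reason for drop-out and SAEs.

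**Step 4: direction and scale.** Let N be the number of patients in the denominator, A the number with at least one related event in the three classes with a route, and B the number whose related events all lie in the fourth class.

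- Overall ADR proportion = (A + B)/N
- Proportion obtainable through the stated routes = A/N
- Shortfall = (A + B)/N − A/N = B/N, which is zero or more

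The documents give neither A nor B. For scale only: if N is taken as the planned 200 (an assumption, since section 9.7.1 names no denominator), each patient in B lowers the percentage by 1/200 = 0.5 percentage points.

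**The case against.** The strongest answer is that ADR here simply means those collected events that are judged to have a reasonable possibility of relationship under section 11.3. On that reading the table is feasible and correct, and all that remains is an undefined term. The first part stands: the output can be produced. The second does not quite follow. Section 9.7.1 does not state the restriction, so the planned output and the collection rules do not match on their face, and a reader of the percentage cannot tell what it leaves out.

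A second objection concerns sections 9.4 and 9.6. A reader might infer from them that other non-serious reactions cannot enter the data at all. The documents do not support that. An ADR tabulation is itself specified in section 9.7.1, so these sections do not clearly bar an ADR field, and the CRF is not among the documents. What can be said is that the protocol states no route for these events.

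Third, section 9.9 (Limitations) reads NA, and a reader might infer that the study report will carry no caveat. That does not follow either. Section 9.9 belongs to the protocol, and section 12.0 says that the report will describe the methodology, so it is free to say which events were collected. The supportable statement is that the protocol plans no caveat.

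Finally, the stakes are low: safety is not among the objectives in section 8.0 or the endpoints in section 9.1, and the output is descriptive. That is accepted and sets the severity.

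**Conclusion.** The point holds and is minor. Under the stated collection rules, the planned ADR percentage, read as an overall one, can be no higher than the true percentage and may be too low. The size cannot be computed from the documents.

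This rests on three assumptions: the CRF follows the routes stated in the protocol, relationship is judged for the collected events as section 11.3 describes, and both percentages use the same denominator.

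Three stronger readings go too far:

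- That the figure must be too low. The shortfall is B/N, and B could be zero.
- That the gap concerns only patients who continue treatment. It also covers those who stop for another cause and events after drop-out.
- That restricting routine collection to SAEs and events that end treatment is itself an error. That is a legitimate choice for an observational study. The fault is only that the planned output does not reflect it.

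**What to change.** In section 9.7.1, replace the ADR output with the number and percentage of patients with:

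- (a) any SAE;
- (b) an SAE with a reasonable possibility of relationship, as defined in section 11.3;
- (c) an adverse event that was the reason for adalimumab discontinuation, and the related ones among these.

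Extend MedDRA coding, now planned for SAEs only, to the events in (c).

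In section 9.9, replace NA with a statement that non-serious adverse events that were not the reason for discontinuation were not systematically collected, and that no overall ADR percentage is therefore reported.

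The cost is a rewording of section 9.7.1, a short statement in section 9.9, and the coding of a few more events. All the listed events already have a collection route, so no new data are needed. The downside is that the report cannot give an overall ADR percentage. If the sponsor wants one, the protocol would have to add an item that collects the missing class, which is a larger change.

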9.8 Quality Control

Prior to the initiation of the study, an investigator's meeting or initiation visit will be held with AbbVie personnel or his/her designee, the investigators and their study coordinators. This meeting will include a review of the protocol and CRF completion.

Investigator must assure that the study is conducted in accordance with the protocol and all relevant regulations and CRF is completed accurately.

In general, monitoring for any site is not required, but, for quality assurance, internal consistency check for completeness and consistency of data will be done to ensure the integrity of the information reported.

CRF will be reviewed by CRAs at AbbVie or their designees for completeness and conclusiveness and when necessary, query will be generated and will be resolved by the site staffs.

All data hand-entered in the database will be verified by a double-key entry procedure. Any discrepancies will be reviewed against the hard copy CRF and corrected. After completion of the entry process, computer logic checks will be run. Any necessary corrections will be made to the database and documented.

9.9 Limitations of the Research Methods

NA

9.10 Other Aspects

NA

10.0 Protection of Human Subjects

The study should receive approval from the Institutional Review Board (IRB) of the each institution, and then a written study agreement should be made with institutions before the initiation of the study in each institution.

Patient written authorization form to use and/or disclose personal and/or health data from patients must be obtained prior to enrolling the patient and the physician is required to document this authorization.

Patient confidentiality must be maintained at all times; therefore demographics that could identify the patients will not be collected.

11.0 Management and Reporting of Adverse Events/Adverse Reactions**11.1 Adverse Event Definition and Serious Adverse Event Categories**

An adverse event (AE) is defined as any untoward medical occurrence in a patient, which does not necessarily have a causal relationship with their treatment. An adverse event can therefore be any unfavorable and unintended sign (including an abnormal laboratory finding), symptom, or disease temporally associated with the use of a medicinal product, whether or not the event is considered causally related to the use of the product.

Such an event can result from use of the drug as stipulated in the labeling, as well as from accidental or intentional overdose, drug abuse, or drug withdrawal. Any worsening of a pre-existing condition or illness is considered an adverse event.

If an adverse event meets any of the following criteria, it is considered a serious adverse event (SAE):

Death of Patient:	An event that results in the death of a patient.
Life-Threatening:	An event that, in the opinion of the investigator, would have resulted in immediate fatality if medical intervention had not been taken. This does not include an event that would have been fatal if it had occurred in a more severe form.
Hospitalization:	An event that results in an admission to the hospital for any length of time. This does not include an emergency room visit or admission to an outpatient facility.
Prolongation of Hospitalization:	An event that occurs while the study patient is hospitalized and prolongs the patient's hospital stay.
Congenital Anomaly:	An anomaly detected at or after birth, or any anomaly that results in fetal loss.
Persistent or Significant Disability/Incapacity:	An event that results in a condition that substantially interferes with the activities of daily living of a study patient. Disability is not intended to include experiences of relatively minor medical significance such as headache, nausea, vomiting, diarrhea, influenza, and accidental trauma (e.g., sprained ankle).
Important Medical Event Requiring Medical or Surgical Intervention to Prevent Serious Outcome:	An important medical event that may not be immediately life-threatening or result in death or hospitalization, but based on medical judgment may jeopardize the patient and may require medical or surgical intervention to prevent any of the outcomes listed above (i.e., death of patient, life threatening, hospitalization, prolongation of hospitalization, congenital anomaly, or persistent or significant disability/incapacity). Additionally, any elective or spontaneous abortion or stillbirth is considered an important medical event. Examples of such events include allergic bronchospasm requiring intensive

treatment in an emergency room or at home, blood dyscrasias or convulsions that do not result in inpatient hospitalization, or the development of drug dependency or drug abuse.

11.2 Severity

The following definitions will be used to rate the severity for any adverse event being collected as an endpoint/data point in the study and for all serious adverse events.

Mild: The adverse event is transient and easily tolerated by the patient.

Moderate: The adverse event causes the patient discomfort and interrupts the patient's usual activities.

Severe: The adverse event causes considerable interference with the patient's usual activities and may be incapacitating or life threatening.

11.3 Relationship to Pharmaceutical Product

The following definitions will be used to assess the relationship of the adverse event to the use of product:

Reasonable Possibility An adverse event where there is evidence to suggest a causal relationship between the product and the adverse event.

No Reasonable Possibility An adverse event where there is no evidence to suggest a causal relationship between the product and the adverse event.

If no reasonable possibility of being related to product is given, an alternate etiology must be provided for the adverse event.

11.4 Serious Adverse Event Collection Period

Serious adverse events will be reported to AbbVie from the time the physician obtains the patient's authorization to use and disclose information (or the patient's informed consent) until 30 days following the intake of the last dose of physician-prescribed treatment.

11.5 Serious Adverse Event Reporting

In the event of a serious adverse event, the physician will:

- For events from patients using and AbbVie product - notify the AbbVie contact person identified below within 24 hours of the physician becoming aware of the event.

11.6 Pregnancy Reporting

In the event of a maternal/paternal pregnancy occurrence in the patient, the physician will notify AbbVie contact person identified in Section 11.5 within 24 hours of the physician becoming aware of the pregnancy and will be requested additional information on the progress and results of the pregnancy including fetus/infant information.

Annex 1.

1) Maastricht Ankylosing Spondylitis Enthesitis Score (MASES)

MAASTRICHT ANKYLOSING SPONDYLITIS ENTHESITIS SCORE				JE
The MASES and Additional Enthesitis score should only be completed for patients with Enthesitis at the screening visit. Please grade each enthesis below 0(absent), 1(present)				
		Patient Right		Patient Left
1st Costochondral joint		 0	 1	 0  1
7th Costochondral joint		 0	 1	 0  1
Posterior Superior Iliac Spine		 0	 1	 0  1
Anterior Superior Iliac Spine		 0	 1	 0  1
Iliac Crest		 0	 1	 0  1
Proximal Insertion of Achilles tendon		 0	 1	 0  1
Patient Midline				
5th Lumbar Spinous process		 0		 1
Total				
ADDITIONAL ENTHESITIS SCORE				JE
		Patient Right		Patient Left
Fascia plantaris		 0	 1	 0  1

2) Joint Evaluation

JOINT EVALUATION		JE					
Joint (circle the correct answer)		0=Absent		1=Present			
		Pain/Tenderness		Swollen			
		R	L	R	L	R	L
1. Sternoclavicular		0	1	0	1	0	1
2. Acromio-clavicular		0	1	0	1	0	1
3. Shoulder		0	1	0	1	0	1
4. Elbow		0	1	0	1	0	1
5. Wrist		0	1	0	1	0	1
6. Metacarpophalangeal I		0	1	0	1	0	1
7. Metacarpophalangeal II		0	1	0	1	0	1
8. Metacarpophalangeal III		0	1	0	1	0	1
9. Metacarpophalangeal IV		0	1	0	1	0	1
10. Metacarpophalangeal V		0	1	0	1	0	1
11. Thumb Interphalangeal		0	1	0	1	0	1
12. Proximal Interphalangeal II		0	1	0	1	0	1
13. Proximal Interphalangeal III		0	1	0	1	0	1
14. Proximal Interphalangeal IV		0	1	0	1	0	1
15. Proximal Interphalangeal V		0	1	0	1	0	1
16. Hip		0	1	0	1	N/A	
17. Knee		0	1	0	1	0	1
18. Ankle		0	1	0	1	0	1
19. Metatarsophalangeal I		0	1	0	1	0	1
20. Metatarsophalangeal II		0	1	0	1	0	1
21. Metatarsophalangeal III		0	1	0	1	0	1
22. Metatarsophalangeal IV		0	1	0	1	0	1

[figure not shown]
Adalimumab
P15-238 Protocol
Version 2.0

23. Metatarsophalangeal V	0	1	0	1	0	1	0	1

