9.0 Research Methods

9.1 Study Design

This is a prospective, mono-country, multi-center study in AS patients treated with adalimumab.

At least 200 subjects will be enrolled at approximately 10 sites.

Physicians will be asked to document on a separate log the number of patients who are possible to participate in this study. Presence or absence of EAMs and decision to participate will be collected.

The baseline assessment should be performed prior to the first dose of adalimumab (Visit1). Study visits will be conducted at 12, 28, 36 and 52 week after baseline. All subjects will have one Follow-up approximately 30days after the last dose of adalimumab.

Primary Endpoint:

- The frequency of EAMs of interest at baseline: peripheral arthritis, enthesitis and dactylitis

Secondary Endpoints:

- The percentage of patients with 50% improvement of baseline BASDAI (BASDAI 50) at week 12, 28, 36, and 52
- The change of MASES (Maastricht Ankylosing Spondylitis Enthesitis Score) from baseline to week 12, 28, 36, and 52 in patients who had enthesitis at baseline
- The percentage of patients who have enthesitis of the plantar fascia from baseline to week 12, 28, 36 and 52.
- The change of dactylitis score from baseline to week 12, 28, 36 and 52 in patients who had dactylitis at baseline.
- The change of tender and swollen joint counts (TJC, 0-46; SJC, 0-44) from baseline to week 12, 28, 36 and 52 in patients who had peripheral arthritis (≥ 1 swollen joint) at baseline.

The prescription of adalimumab is at the discretion of the physician in accordance with clinical practice and label, is made independently from this study and precedes the decision to offer the patient the opportunity to participate in this study.

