9.7 Data Analysis

The study population will be classified by ITT (Intention-To-Treat) set and PP (Per-Protocol) set.

- ITT set: The ITT set will consist of those patients who have received at least one adalimumab treatment and have assessed EAMs at baseline.

- PP set: The PP set will consist of those patients who meet inclusion/exclusion criteria and complete the study without any major protocol deviation of the patients included in the ITT set.

General Considerations

Continuous variables will be described with the number of patients, arithmetic mean, standard deviation, median, minimum, and maximum. For categorical variables, the frequency and proportion will be presented. The values such as arithmetic mean, standard deviation, and proportion will be rounded to two decimal places. If the observation value is missing value, it will be treated as a missing value in the analysis.

Baseline Characteristics including demographics

Descriptive statistics will be used to present variables regarding demographics and disease/medication related data. Continuous variables will be described with the number of patients, arithmetic mean, standard deviation, median, minimum and maximum. For categorical variables, the frequency and proportion will be presented. The values such as arithmetic mean, standard deviation, and proportion will be rounded to two decimal places.

If the observation value is missing value, it will be treated as a missing value in the analysis. Statistical analyses will be performed using SAS V9.2 or higher.

Primary Endpoint:

The frequency of EAMs of interest at baseline: peripheral arthritis, enthesitis and dactylitis

-The frequency and the proportion of patients who are having peripheral arthritis, enthesitis or dactylitis in Korean AS patients at baseline will be presented, and 95% confidence intervals will be calculated.

Secondary Endpoints:

- The percentage of patients with 50% improvement of baseline BASDAI (BASDAI 50) at week 12, 28, 36, and 52
 - The frequency and the proportion of patients with 50% improvement of baseline BASDAI at week 12, 28, 36, 52 will be presented.
- The change of MASES (Maastricht Ankylosing Spondylitis Enthesitis Score) from baseline to week 12, 28, 36, and 52 in patients who had enthesitis at baseline
 - The descriptive statistics (the number of patients, mean, standard deviation, median, min, max) for MASES according to study visit and the change from baseline at week 12, 28, 36, 52 will be presented.

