- The percentage of patients who have enthesitis of the plantar fascia from baseline to week 12, 28, 36 and 52.
 - The frequency and the proportion of patients who have enthesitis of the plantar fascia at week 12, 28, 36, 52 will be presented.
- The change of dactylitis score from baseline to week 12, 28, 36 and 52 in patients who had dactylitis at baseline.
 - The descriptive statistics (the number of patients, mean, standard deviation, median, min, max) for dactylitis score according to study visit and the change from baseline at week 12, 28, 36, 52 will be presented.
- The change of tender and swollen joint counts (TJC, 0-46; SJC, 0-44) from baseline to week 12, 28, 36 and 52 in patients who had peripheral arthritis (≥ 1 swollen joint) at baseline.
 - The descriptive statistics (the number of patients, mean, standard deviation, median, min, max) for tender and swollen joint counts (TJC, 0-46; SJC, 0-44) according to study visit and the change from baseline at week 12, 28, 36, 52 will be presented.

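### Annex 1 limits MASES and plantar-fascia scoring to patients already known to have enthesitis, contradicting Section 9.3; about 94 of 200 patients would have no follow-up plantar-fascia score

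*Combined protocol and SAP*

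**What the plan says.** The instruction is printed on the scoring form in Annex 1: "The MASES and Additional Enthesitis score should only be completed for patients with Enthesitis at the screening visit". The Additional Enthesitis score on that form is the plantar-fascia item, right and left.

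Section 9.3 reads differently in three respects.

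- **Definition.** "Enthesitis is defined as at least 1 inflamed enthesis in the Maastricht Ankylosing Spondylitis Enthesitis Score (MASES, 0 to 13) or of the plantar fascia". The scores on the form are what establish the diagnosis.
- **Baseline.** Item 5 collects "Extra-axial symptoms: Enthesitis, Peripheral arthritis and Dactylitis (presence or absence"). Item 6 separately lists MASES and plantar-fascia enthesitis, with no subgroup restriction.
- **Follow-up.** Both scores are listed again for weeks 12, 28, 36 and 52, also unrestricted. The text adds: "Dactylitis score and the presence of plantar fascia will be evaluated to investigate the effectiveness of adalimumab on EAMs".

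The schedule in Section 9.1 starts at baseline: "The baseline assessment should be performed prior to the first dose of adalimumab (Visit1"). No screening visit is defined.

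Section 9.1 states the plantar-fascia endpoint as "The percentage of patients who have enthesitis of the plantar fascia from baseline to week 12, 28, 36 and 52", and Section 9.7 analyses it as follows: "The frequency and the proportion of patients who have enthesitis of the plantar fascia at week 12, 28, 36, 52 will be presented". Neither limits it to patients with enthesitis at baseline. The MASES, dactylitis and joint-count endpoints each do carry such a limit. The general rule for blanks in Section 9.7 is: "If the observation value is missing value, it will be treated as a missing value in the analysis".

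**The concern.** The Annex rule is circular: enthesitis must be known before the form that defines it is completed. It also hangs on a visit that does not exist.

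The endpoint most exposed is the plantar-fascia percentage, which serves the secondary objective on the effectiveness of adalimumab on extra-axial manifestations (EAMs). If all patients are scored at baseline but only the enthesitis subgroup afterwards, the two percentages have different denominators. A real improvement can then be hidden, and a stable rate can look like worsening. If blanks are instead counted as absent, new onset in the unscored patients is never seen.

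The primary endpoint is exposed conditionally. Enthesitis is one of its three manifestations and the one that needs the larger sample (171 against 144). Under the Annex, a patient recorded as having no enthesitis need have no completed score form behind that entry.

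**Working it through.** **Inputs.** N = 200 (Section 9.1). Enthesitis 53%, 95% confidence interval of full width 15%, drop-out 20% (Section 9.5). Alternative enthesitis rate 42.7% (Section 7.1). The documents give no plantar-fascia rate, new-onset rate or sensitivity of an unscored judgement; values used for these are assumptions.

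**1. The plan's own sample size.** n = 1.96² × p(1 − p) / 0.075².
- p = 0.53: 170.1, rounded up to 171.
- p = 0.70: 143.4, rounded up to 144.

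Both stated figures reproduce, so the planned half-width is 7.5 points.

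**2. Possible readings of the Annex sentence.**
- *It applies at every visit:* patients judged free of enthesitis have no scores at all, against Section 9.3 at baseline and follow-up.
- *It limits follow-up only:* this suits the MASES change endpoint, which is already restricted to patients with baseline enthesitis. It does not suit the plantar-fascia endpoint, which is unrestricted.
- *The form is completed only at screening:* no follow-up MASES would exist, which conflicts with Section 9.3 even more.

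No reading agrees with the body of the protocol.

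**3. Patients without a follow-up plantar score,** baseline status judged correctly: N × (1 − p).

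| | 53% enthesitis | 42.7% enthesitis |
|---|---|---|
| 200 patients | 94 | 114.6 |
| 160 after drop-out | 75.2 | 91.7 |

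**4. Blanks treated as missing, no new onset.** The denominator falls from 200 to 200 × 0.53 = 106, so percentages are multiplied by 1/0.53 = 1.89.
- Assumed whole-sample rates of 10%, 20% and 30% are reported as 18.9%, 37.7% and 56.6%.
- All patients scored at baseline, rate unchanged at 20%: 40/200 = 20.0% at baseline, 40/106 = 37.7% at follow-up.
- All patients scored at baseline, true fall from 20% to 10.6%: follow-up is 21.2/106 = 20.0%, reported as no change.

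**5. Blanks counted as absent.** With assumed new onset of 2%, 5% and 10% among the 94, the cases missed are 94 × 0.02, 0.05 and 0.10 = 1.9, 4.7 and 9.4. Divided by 200, that is 0.9, 2.4 and 4.7 points.

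**6. Primary frequency, if presence or absence is recorded without the full examination.** Shortfall = 0.53 × (1 − s); unscored patients = 200 × (1 − 0.53s).

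| Assumed sensitivity s | Shortfall (points) | Unscored of 200 |
|---|---|---|
| 95% | 2.7 | 99 |
| 90% | 5.3 | 105 |
| 70% | 15.9 | 126 |

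The shortfall equals the 7.5-point half-width at s = 1 − 0.075/0.53 = 0.858.

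**The case against.** The conflict of wording is hard to dispute; the consequences can be argued.

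- **Primary endpoint.** Section 9.3 collects presence or absence as its own item, and its definition already requires the sites to be examined before absence is recorded. Understatement therefore needs a site to depart from Section 9.3. The direction is not fixed either: leaving unscored patients out of the ITT set, which requires EAMs to have been assessed at baseline, would overstate the frequency. This stands, and is why the primary harm is put as conditional. The loss of traceability remains in both directions.
- **The 37.7% example depends on the reading.** If the Annex is applied at baseline too, baseline is also 40/106 = 37.7% and there is no false rise. True, but both percentages are then inflated as estimates for the study population. Section 9.7 also reports counts, which would show 40 falling to about 21; a reader of the percentages would still be misled.
- **The information lost is narrow.** A patient correctly classed as free of enthesitis has no plantar involvement at baseline, so only new onset is lost. This is right for the information itself, but does not mend the changed denominator.
- **Checks exist.** Section 9.4 requires source documents and Section 9.8 provides for CRF review. Section 9.8 also says site monitoring is generally not required, so the form carries much of the burden.
- **The endpoint may be the slip.** Three other EAM endpoints are limited to patients affected at baseline, so the limit may have been left off the plantar one. That is possible, but the unrestricted listing in Section 9.3 would still contradict the Annex.
- **Weight.** This is a descriptive study and the item is one of five secondary endpoints. That limits the severity, not the need to reconcile the text.

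**Conclusion.** The concern holds. Annex 1 and Section 9.3 cannot both be followed, and every reading of the Annex conflicts with the body of the protocol.

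At 53% enthesitis and correct baseline classification, 94 of 200 patients would have no follow-up plantar-fascia score. Across the documents' two enthesitis rates, with and without drop-out, the number is about 75 to 115. The 1.89-fold inflation assumes that blanks are treated as missing and that there is no new onset. The false rise or hidden fall also assumes that everyone is scored at baseline. Understatement of the primary frequency is possible rather than certain, and reaches the planned half-width only at about 86% sensitivity or lower.

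This should be fixed. Confidence is high for the contradiction; the sizes rest on the assumptions named.

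**What to change.** - **Annex 1:** replace the instruction with wording such as: *Complete MASES and the plantar-fascia score for all subjects at baseline (Visit 1) and at weeks 12, 28, 36 and 52.* This also removes the reference to a screening visit.
- **Baseline status:** derive enthesitis present or absent from these scores, using the Section 9.3 definition.
- **Section 9.7:** state that the denominator of the plantar-fascia percentage is all patients assessed at that visit, and show the number not assessed.
- **MASES change endpoint:** leave it restricted to patients with enthesitis at baseline.

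The cost is one sentence in Annex 1, a denominator sentence in Section 9.7, a line on the derivation, and a notice to about 10 sites. No procedure is added, because Section 9.3 already lists both assessments at each of these visits. The notice should go out promptly, since scores not taken at a visit cannot be recovered later.
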